### **Exclusion of PK parameters**

The ADS ADPP contains column variables APEXC and APEXCO indicating inclusion/exclusion (APEXC) of a PK parameter and an analysis flag comment (APEXCO). All analyses based on the PKS are based on PK parameter values which are not flagged for exclusion, i.e. with APEXC equal to "Included".

Exclusion of plasma concentrations

The ADS ADPC (PK concentrations per time-point or per time-interval) contains column variables ACEXC or ACEXCO indicating inclusion/exclusion (ACEXC) of a concentration and an analysis flag comment (ACEXCO). Exclusion of a concentration depends on the analysis flag comment ACEXCO. For example, if ACEXCO is set to "ALL CALC", the value will be excluded for all types of analyses based on concentrations. If ACEXCO is set to "DESC STATS" the value will be excluded from descriptive evaluations per planned time point/time interval. If ACEXCO contains the addition "TIME VIOLATION" or "TIME DEVIATION", the value can be used for further analyses based on actual times. If ACEXCO is set to "HALF LIFE", the value will be excluded from half-life calculation only; the value is included for all other analyses.

Further details are given in 001-MCS-36-472\_RD-01 "Noncompartmental Pharmacokinetic / Pharmacodynamic Analyses of Clinical Studies" (4) and 001-MCS-36-472\_RD-03 "Description of Analytical Transfer Files and PK/PD Data Files" (5).

## **7.7 EXTENT OF EXPOSURE**

Descriptive statistics are planned for this section of the CTR based on the TS. The number of days taking medication will be analysed with standard descriptive statistical parameters and also using frequency tables for categories "<28 days", "28 days" and "> 28 days".

The date and time of drug administration will be listed for each subject.

## **7.8 SAFETY ANALYSIS**

All safety analyses will be performed on the TS.

### **7.8.1 Adverse events**

AEs will be coded with the most recent version of MedDRA.

The analyses of AEs will be descriptive in nature. All analyses of AEs will be based on the number of subjects with AEs and not on the number of AEs.

For analysis, multiple AE occurrence data on the eCRF will be collapsed into one event provided that all of the following applies:

- All AE attributes are identical (lower level term, intensity [CTCAE grade Version 4.03], action taken, therapy required, seriousness, reason for seriousness, relationship, outcome, AESI)
- The occurrences were time-overlapping or time-adjacent (time-adjacency of two occurrences is given if the second occurrence started at most 1 hour after the first occurrence ended)

For further details on summarization of AE data, please refer to 'Handling and summarization of adverse event data for clinical trial reports and integrated summaries' ([6](#)) [001-MCG-156] and "Handling of missing and incomplete AE dates" ([3](#)) [001-MCG-156\_RD-01].

The analysis of AEs will be based on the concept of treatment emergent AEs. That means that all AEs will be assigned to the screening phase or on-treatment phase as defined in [Section 6.1](#).

An overall summary of AEs will be presented. This overall summary will comprise summary statistics for the class of other significant AEs according to ICH E3 and for the class of AESIs.

**CTP:** *The following are considered as AESIs in this trial:*

*Hepatic injury*

*A hepatic injury is defined by the following alterations of hepatic laboratory parameters:*

- *an elevation of AST and/or ALT > 3 fold upper limit normal (ULN) combined with an elevation of total bilirubin > 2 fold ULN measured in the same blood draw sample, and/or*
- *marked peak aminotransferase (ALT and/or AST) elevations  $\geq 10$  fold ULN*

The investigator had to classify on the eCRF whether an observed AE was an AESI or not.

According to ICH E3 (8), AEs classified as ‘other significant’ need to be reported and will include those non-serious and non-significant AEs

- (i) which are marked haematological or other lab abnormalities, or
- (ii) which were reported with ‘action taken = discontinuation’ or ‘action taken = reduced’, or
- (iii) which lead to significant concomitant therapy as identified by the Clinical Monitor/Investigator at a Medical Quality Review Meeting.

The frequency of subjects with AEs will be summarised by treatment, primary SOC and preferred term. AEs which were considered by the investigator to be drug related (primary endpoint) will be summarised separately. Separate tables will also be provided for subjects with SAEs, subjects with AESIs and subjects with other significant AEs (according to ICH E3 (8)). The frequency of subjects with AEs and the frequency of subjects with AEs considered by the investigator to be drug related will also be summarised by maximum grade of CTCAE (version 4.03), primary SOC and preferred term.

The SOCs will be sorted according to the standard sort order specified by the EMA, preferred terms will be sorted by total frequency (within SOC).

For disclosure of AE data on ClinicalTrials.gov, the frequency of subjects with non-serious AEs occurring with an incidence of greater than 5 % (in preferred terms) will be summarised by treatment, primary SOC and preferred term. The frequency of subjects with SAEs will also be summarised.

For disclosure of AE data in the EudraCT register, the frequency of AEs, the frequency of non-serious AEs with an incidence of greater than 5 % (in preferred terms) and the frequency of SAEs will be summarised.

## **7.8.2     Laboratory data**

The analyses of laboratory data will be descriptive in nature and will be based on BI standards ([7](#)). Laboratory analyses will be based on normalised values, i.e., for a given laboratory parameter, values will be transformed to a standard unit and a standard reference range before statistical analysis.

**CTP:** *Laboratory data will be compared to their reference ranges. Values outside the reference range will be flagged. Additionally, differences from baseline will be evaluated.*

Descriptive statistics of laboratory values over time and for the difference from baseline (see [Section 6.7](#)) will be provided. Frequency tables of changes between baseline and last value on treatment with respect to the reference range will be presented.

Possibly clinically significant abnormal laboratory values are only those identified either in the Investigator's comments or at the RPM/DBLM at the latest. It is the Investigator's responsibility to decide whether a lab value is clinically significant abnormal or not. Standard or project-specific rules for flagging clinically significant values in an automated manner will not be applied in this study.

Clinically relevant findings in laboratory data will be reported as baseline conditions (at screening) or as AEs (during the trial) if judged clinically relevant by the investigator, and will be analysed as such.

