		647:55	08:55		x ^{14, 15}	▼	x ^{14, ,16}				
		648:00	09:00	Last drug administration		▲					
		648:15	09:15		x				x		
		648:30	09:30		x ¹⁵		x	x	x	x	
		648:45	09:45		x				x	x	
		649:00	10:00		x ¹⁵		x	x	x	x	x
		649:30	10:30		x				x		
		650:00	11:00	240 mL fluid intake and light breakfast ³	x ¹⁵		x	x	x	x	x
		651:00	12:00		x						
		652:00	13:00	240 mL fluid intake, thereafter lunch ³	x ¹⁵	+	x	x	x	x	x
		654:00	15:00		x ¹⁵		x				
		656:00	17:00	Snack (voluntary) ³	x ¹⁵	+		x	x	x	x
		658:00	19:00	Dinner ³	x ¹⁵		x				
		660:00	21:00		x ¹⁵	+	x	x	x	x	x
	29	672:00	09:00		x ¹⁵	▼	x	x	x	x	x
		673:00	10:00	Discharge from trial site (confirmation of fitness) ⁴							
30	696:00	09:00	Ambulatory visit ¹⁷	x	x ¹⁵		x	x	x	x	x
32+-1	744:00	09:00	Ambulatory visit ¹⁷		x ¹⁵		x				x
36+-2	840:00	09:00	Ambulatory visit ¹⁷		x ¹⁵		x				
40	936:00	09:00	Ambulatory visit		x ¹⁵		x				
3	42 to 48		End of trial (EOT) examination ^{4,12}	x				x	x	x	x

1. Screening includes subject information, informed consent, physical examination, check of vital signs, ECG, safety laboratory (including exclusionary laboratory tests), demographics (including determination of body height and weight, smoking status and alcohol history), relevant medical history, concomitant therapy and review of inclusion/exclusion criteria.
2. The time is approximate; the respective procedure is to be performed and completed within 3 h prior to drug administration. Allocation to treatment may be performed at any time following enrolment but must be completed prior to (first) drug administration.
3. If several actions are indicated at the same time point, the intake of meals will be the last action.
4. End of trial examination includes physical examination, body weight, vital signs, ECG, safety laboratory, recording of AEs and concomitant therapies. Confirmation of fitness includes physical examination.
5. Urine drug screening and alcohol breath test will be done at screening and Day -1.
6. AEs and concomitant therapies will be recorded throughout the trial, but will be specifically asked for at the time points indicated in the [Flow Chart](#) above.
7. Safety laboratory, ECG, blood pressure assessment and AE questioning to be done and medically evaluated within 3 days prior to first administration of study drug; this visit can be omitted, if the screening examination is performed on Days -3, -2 or -1.

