3.3.4 Removal of subjects from therapy or assessments

3.3.4.1 Removal of individual subjects

An individual subject is to be removed from the trial if:

1. The subject withdraws consent, without the need to justify the decision
2. The subject needs to take concomitant drugs that interfere with the investigational product or other trial medication
3. The subject is no longer able to participate for other medical reasons (such as surgery, adverse events, or diseases)
4. An AE or clinically significant laboratory change or abnormality occurred that the investigator judges to warrant discontinuation of treatment. This may include cases of sustained symptomatic hypotension (BP <90/50 mmHg) or hypertension (BP >180/100 mmHg) or of clinically relevant changes in ECG requiring intervention as well as unexplained liver enzyme elevations at any time during the trial.

In addition to these criteria, the physician may discontinue subjects at any time based on his or her clinical judgment.

A subject can also be removed from the trial if eligibility criteria are being violated or if the subject fails to comply with the protocol (for instance, by non-adherence to dietary rules, or non-attendance at study assessments).

Proprietary confidential information © 2017 Boehringer Ingelheim International GmbH or one or more of its affiliated companies

If a subject is removed from or withdraws from the trial prior to first administration of trial medication, the data of this subject will not be entered in the case report form (CRF) or trial database and will not be reported in the clinical trial report (CTR). The only exception to this rule is when the subject had an AESI and/or SAE that the investigator considers related to the screening procedure. If a subject is removed from or withdraws from the trial after first administration of trial medication, this will be documented and the reason for discontinuation must be recorded in the CRF. In this case, the data will be included in the CRF/trial database and will be reported in the CTR. At the time of discontinuation a complete EOT examination will be performed if possible and the information will be recorded in the CRFs. These discontinuations will be discussed in the CTR.

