6. INVESTIGATIONAL PLAN

6.1 VISIT SCHEDULE

All visits must be performed as specified in Flow Chart. The investigator/sponsor can decide to perform an unscheduled visit if deemed necessary for any valid reasons.

Further details of measurement performed during the study are specified under [Section 5](#).

Time windows are permitted as follows:

- General medical examination: at screening (1 to 21 days prior to Day1) and at the end-of-trial evaluation (within 14 to 20 days after last drug administration).
- BP and PR: ± 15 min (0:30, 0:45, 1:00, 2:00) and ± 30 min (4:00, 8:00, 12:00) on Day 1, Day 14 and Day 28, ± 60 min on other days and up to 3 hours prior to drug administration if indicated "before drug administration"
- ECG: ± 15 min (0:15, 0:30, 0:45, 1:00, 1:30, 2:00) and ± 30 min (4:00, 8:00, 12:00) on Day 1, Day 14 and Day 28, ± 60 min on other days.
ECGs on Day 1, 2, 14, 15, 28 and 29: for the second and third ECG a time interval of 1-3 min between ECGs should be maintained
- Laboratory/urinalysis: Up to 3 hours prior to drug administration if indicated "before drug administration". Urinalysis test can be done up to 3 hours prior to drug administration at some other time points indicated in the flow chart.
- Pharmacokinetic blood sampling for predose concentration in multiple dose part: ± 5 min (has to be done before drug administration)

Other pharmacokinetic blood sampling / urine collection: For planned individual plasma concentration sampling times refer to Flow Chart. While these nominal times should be adhered to as closely as possible, the actual sampling times will be recorded and used for the calculation of pharmacokinetic parameters.

The designation "before" on Day 1 refers to the time period of 3 hours before drug administration (see [Flow Chart](#)), i.e., study measurements and assessments scheduled to occur "before" have to be performed and completed within 3 hours prior to drug administration.

Relevant time violations will be identified and their handling discussed no later than at the (B)RPM.

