7.3.3 Safety analyses

Safety will be assessed for the primary endpoint and parameter of interest listed in [Section 5.2.1](#). All treated subjects (that is, all subjects who received at least one dose of study drug), will be included in the safety evaluation. Safety analyses will be descriptive in nature and will be based on BI standards.

Treatments will be compared in a descriptive way. The placebo control group in the safety evaluation will consist of all placebo treated subjects, regardless of the dose group in which they were treated. The active treatment groups will be compared to the placebo group in a descriptive way. Tabulations of frequencies/proportions will be used for the evaluation of categorical (qualitative) data, and tabulations of descriptive statistics will be used to analyse continuous (quantitative) data.

The analyses will be done by 'treatment at onset'.

Measurements (such as ECG, vital signs, or laboratory parameters) or AEs will be assigned to treatments (see [Section 4.1](#)) based on the actual treatment at the planned time of the measurement or on the recorded time of AE onset (concept of treatment emergent AEs). Therefore, measurements planned or AEs recorded prior to first intake of trial medication will be assigned to 'screening', those between first trial medication intake until the trial termination date will be assigned to the treatment period. These assignments including the corresponding time intervals will be defined in detail in the TSAP.

Adverse events will be coded using the Medical Dictionary for Regulatory Activities (MedDRA). Frequency, intensity according to CTCAE grading and causal relationship of AEs will be tabulated by treatment, primary system organ class and preferred term. SAEs,

Proprietary confidential information © 2017 Boehringer Ingelheim International GmbH or one or more of its affiliated companies

AESIs (see [Section 5.2.2.1](#)) and other significant AEs (according to ICH E3) will be listed separately.

Laboratory data will be compared to their reference ranges. Values outside the reference range will be flagged. Additionally, differences from baseline will be evaluated.

For vital signs, the differences from baseline will be evaluated.

The derivation of the quantitative and qualitative ECG endpoints and their analyses will be described in the TSAP.

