## **6. GENERAL ANALYSIS DEFINITIONS**

### **6.1 TREATMENTS**

For basic study information on treatments to be administered, assignments of dose groups, and selection of doses, cf. Section 4 of the CTP.

Subjects were treated with 3 mg, 6 mg or 10 mg of BI 1467335 (test treatment, T) or placebo (reference treatment, R) once daily over 28 days. Three placebo groups will be defined: Placebo for Japanese, Placebo for Caucasians and Total placebo. Placebo for Japanese will be defined as a pooled group of the Japanese subjects receiving placebo treatment in the three dose groups. Placebo for Caucasians will be defined as the placebo subjects in the 10 mg dose group for Caucasians (which comprises all placebo-treated Caucasian subjects). Total placebo will be defined as one pooled placebo group (i.e. no distinction between dose groups and ethnicity will be made for placebo subjects).

For statistical analysis of AEs, safety laboratory data, vital signs and ECG, the following analysis phases are defined for each subject:

Table 6.1: 1 Flow chart of analysis phases for statistical analyses of AEs, safety laboratory data, vital signs and ECG

| Study analysis phase | Label  | Start (inclusive)                               | End (exclusive)                                    |
|----------------------|--|---|--|
| Screening            | Screening  | Date of informed consent                        | Date/time of first administration of study drug    |
| On-treatment         | Placebo,
3 mg BI for
Japanese,
6 mg BI for
Japanese,
10 mg BI for
Japanese
or 10 mg BI for
Caucasians,
respectively | Date/time of first administration of study drug | 0:00 on day after subject's trial termination date |

CTR Section 15, Appendix 16.1.9.2.8.2 and Appendix 16.1.9.2.8.3 AE displays will present results for the on-treatment phase only.

In CTR Section 15 AE tables (but not in Appendix 16.1.9.2.8.2 and Appendix 16.1.9.2.8.3 AE tables), the following totals will be provided in addition:

- "**Total BI**", defined as the total over all on-treatment phases involving BI, i.e., "3 mg BI for Japanese" + "6 mg BI for Japanese" + "10 mg BI for Japanese" + "10 mg BI for Caucasians"
- "**Total BI for Japanese**", defined as the total over all on-treatment phases involving BI, i.e., "3 mg BI for Japanese" + "6 mg BI for Japanese" + "10 mg BI for Japanese"

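### As defined in the visible text, the laboratory shift tables labelled on-treatment use, for completers, the end-of-trial value taken 14 to 20 days after the last dose; separately, SAP 5.4.2 and 7.8.5 disagree on slit-lamp output

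*SAP*

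**What the plan says.** **Laboratory shift tables.** SAP 7.8.2 plans this output: "Frequency tables of changes between baseline and last value on treatment with respect to the reference range will be presented". That section does not say where treatment ends.

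SAP 6.1 supplies the only visible definition, and it covers laboratory data by name: "For statistical analysis of AEs, safety laboratory data, vital signs and ECG, the following analysis phases are defined for each subject". Table 6.1: 1 has two phases, screening and on-treatment. The second ends (exclusive) at "0:00 on day after subject's trial termination date". There is no follow-up phase.

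Protocol 7.3.3 agrees: "Measurements (such as ECG, vital signs, or laboratory parameters) or AEs will be assigned to treatments", and "those between first trial medication intake until the trial termination date will be assigned to the treatment period". Protocol 5.2.2.2 explains the trial termination date as the last contact under the protocol. It gives the reason for the long window, for adverse events (AEs): the residual effect period is not yet known.

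For a completer, the last protocol contact is the EOT visit, Day 42 to 48 in the Flow Chart. Protocol 6.1 places the general medical examination "at the end-of-trial evaluation (within 14 to 20 days after last drug administration". Flow Chart footnote 4 confirms that blood is taken: "End of trial examination includes physical examination, body weight, vital signs, ECG, safety laboratory, recording of AEs and concomitant therapies". For subjects who stop early, Protocol 3.3.4.1 says: "At the time of discontinuation a complete EOT examination will be performed if possible".

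**Slit lamp.** SAP 5.4.2 says that ophthalmological findings will be presented with descriptive statistics and refers to Protocol 5.2.5.3 for the definition. SAP 7.8.5 says that such findings are reported and summarised as baseline conditions or AEs, and that they get no listing or analysis of their own. Protocol 5.2.5.3 gives the timing and purpose of the examination, but no form of presentation.

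**The concern.** A long window works differently for AE counts and for a last-value table. For AE counts, extending the window can only add events, which is cautious when the residual effect period is unknown. In a last-value table, extending the window replaces an earlier value with a later one. If a laboratory value is out of range at the end of dosing and normal two to three weeks later, the table shows no shift although its label says on treatment.

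A second effect is that one column may mix timings. Completers contribute a value well after dosing, while early stoppers may contribute one close to their last dose.

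Safety is the primary objective, and SAP 7.8.2 names no other frequency table against the reference range. A reader of the trial report could take the shift table as a description of the treatment period.

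For the slit lamp, reporting only findings gives no count of subjects examined after treatment. A report with no cataract findings then cannot be told apart from one in which some examinations were not done.

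**Working it through.** **1. Reproducing the plan's interval.** The Flow Chart puts the last dose at 648:00 h on Day 28 and EOT on Day 42 to 48. Planned hour of day d = (d − 1) × 24.

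- Day 28: 27 × 24 = 648 h, as stated.
- Day 42: 41 × 24 = 984 h; 984 − 648 = 336 h = 14 days after the last dose.
- Day 48: 47 × 24 = 1128 h; 1128 − 648 = 480 h = 20 days after the last dose.

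This matches the 14 to 20 days in Protocol 6.1.

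**2. Share of the interval that lies after dosing.** First dose to EOT is 41 to 47 days.

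- 14/41 = 34.1%
- 20/47 = 42.6%

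These are shares of time, not of subjects or of shifts.

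**3. Samples displaced by the EOT value.** The Flow Chart columns are broken in the text, but it appears to show safety laboratory samples at 646:00 on Day 28 and 696:00 on Day 30.

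- Day 28: 648 − 646 = 2 h before the last dose.
- Day 30: 696 − 648 = 48 h after the last dose.
- EOT follows the Day 30 sample by 42 − 30 = 12 to 48 − 30 = 18 days.

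**4. What the shift table shows.** Take a completer with a normal baseline and an EOT sample:

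| Pattern | Last value = EOT | Last value up to Day 30 |
|---|---|---|
| Out of range on Day 30, normal at EOT | no shift | shift |
| Out of range on Day 30 and at EOT | shift | shift |
| Normal on Day 30, out of range at EOT | shift | no shift |
| Out of range mid-treatment, normal from Day 28 on | no shift | no shift |

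The first row is the concern. The third shows why the EOT table should be kept. The fourth is a limit of any last-value table and cannot be blamed on the EOT window.

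**5. Subjects to whom the rule applies.** As planned, 4 × 9 = 36 on active drug and 4 × 3 = 12 on placebo, 48 in all, if every subject completes. The documents give no rate from which to derive the number of affected shifts.

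**6. Slit lamp.** This part is a comparison of wording. SAP 5.4.2 commits to descriptive statistics; SAP 7.8.5 excludes a separate analysis. Summarising findings only as AEs or baseline conditions could satisfy both, but the SAP does not say that this is meant. Up to 48 post-treatment examinations are planned, from Day 29 to EOT.

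**The case against.** **The window is deliberate and consistent.** This stands. Protocol and SAP agree, and the unknown residual effect period is a good reason for a long AE phase. A reader might infer that the documents contradict each other or that the phase is wrong; they do not, and nothing shows that it is. Only its effect on a last-value table is in question, and the visible text does not discuss that.

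**Relevant material is not supplied.** This also stands. SAP 7.8.2 relies on the sponsor's laboratory standard and SAP 6.1 on the ADS Plan. Either may define the term more narrowly, so the EOT reading holds only for the visible definitions.

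**Nothing is lost.** This largely stands. By-visit statistics, differences from baseline, reference-range flags and individual listings remain. Values judged clinically relevant become AEs, and possibly significant values can be identified from investigator comments or at the report planning or database lock meeting. A reader might infer that abnormalities are hidden from the report or that the primary endpoint is biased; the documents support neither.

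**A new cut-off after dosing would be arbitrary.** This stands against replacing the existing table or imposing a fixed limit of, say, 2 days on early stoppers, which the documents do not support. It does not stand against adding a second table built on scheduled samples.

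**The slit-lamp issue is only wording, and missed examinations are handled elsewhere.** This stands in part. A missed examination is a protocol deviation, and SAP 6.2 allows the list of important violations to be extended. But the only entry under missing data in Table 6.2: 1 concerns PK sampling, with PD handling left to the meeting, so no count of examined subjects is planned. A reader might infer that positive findings would go unreported. They would not: SAP 7.8.5 reports them as baseline conditions or AEs.

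**Conclusion.** The point holds and is minor. Under the visible definitions, the laboratory shift tables compare baseline with a value taken 14 to 20 days after the last dose for every completer with an EOT sample. A shift at Day 28 or Day 30 that resolves by EOT appears as no shift. One display is affected, and its numerical effect cannot be derived.

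The conclusion assumes that the trial termination date of a completer is the EOT visit, that the EOT sample is available, and that neither the ADS Plan nor the laboratory standard narrows the term. The placing of the Day 28 and Day 30 samples also assumes that the broken Flow Chart has been read correctly.

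The two SAP statements on slit-lamp output need to be reconciled whichever laboratory definition applies.

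**What to change.** In SAP 7.8.2:

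- Keep the agreed phase definition and the existing table from baseline to last value. Label it as including the EOT value.
- Add a shift table from baseline to the last scheduled laboratory value up to and including the Day 30 sample. For early stoppers, use the last available value and footnote its time since the last dose.
- If the ADS Plan or the laboratory standard already uses a narrower definition, state it here.

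Leave the AE phase unchanged.

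Reconcile SAP 5.4.2 with 7.8.5, preferably with one table by treatment of the post-treatment slit-lamp examination: no finding, finding, not done.

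The cost is SAP wording, one extra set of shift tables, one small slit-lamp table and a footnote. All of it comes from examinations already planned.
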